5.9.1 Prior and Concomitant Therapies

All prior therapies for COPD taken in the 3 months prior the first study treatment administration and all concomitant COPD therapies for will be recorded in the eCRF, with the medication, dose, route and start and stop date(s) and time(s) clearly recorded to document all required washout periods and compliance with the inclusion and exclusion criteria.

Oral therapies for COPD (e.g. oral steroids, theophylline, and roflumilast) are not allowed in the 3 months prior to screening and throughout the study. Inhaled steroids may continue during the study at a maintenance dose.

All long acting (once or twice daily) bronchodilators will be stopped at the screening visit and are not allowed during the study. Patients should not use a long acting bronchodilator (long acting muscarinic antagonists [LAMA], long acting beta2-agonists [LABA], or combination LABA/inhaled steroid) on the day of screening.

Patients taking LAMAs and LABAs should be placed on short acting bronchodilators (e.g. salbutamol, ipratropium or Combivent[®]) as per the discretion of the Investigator. These can be dosed on a regular scheduled basis and/or as needed use. Patients taking LABA/inhaled steroid combination products should be prescribed the inhaled steroid at the same or equivalent dose contained in the combination product to allow continuation of steroid use regularly throughout the study whilst stopping the LABA component. Patients currently taking terbutaline will be switched to other short acting bronchodilators (e.g. salbutamol).

If this is inadequate to control their symptoms, they should contact the Investigator. No scheduled use of salbutamol or ipratropium is allowed during the 3-day treatment periods; but may be used as a rescue medication (see Section 5.10). Salbutamol and ipratropium (or Combivent[®]) must be withheld for at least 8 hours prior to spirometry and this confirmed in the eCRF at the start of each treatment period. If this withhold is not met, the patient should be rescheduled for a repeat visit within permitted windows. Short acting bronchodilators

should be withheld during each treatment period for the time periods stated below unless absolutely necessary:

- 8 hours prior to pre-dose spirometry for Day 1, Day 2 and Day 3.
- Post-dose:
 - Day 1 until after +12 hours spirometry
 - Day 2 until after + 4 hours spirometry
 - Day 3 until after + 24 hours spirometry

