10.3.2 Secondary Endpoints

- Determination of AUC_{0-4h} FEV₁ after morning dosing
- Peak FEV₁ (measured in first 4 hours after dosing) and AUC_{0-12h} FEV₁. These will be measured after dosing on Day 1.
- Determination of onset of action (>10% increase in FEV₁, from pre-first dose, censored at 120 minutes) on Day 1
- RV, FRC and sG_{aw} at 1.25 hours after dosing on Day 2
- RPL554 steady state pharmacokinetics (AUC, C_{max}, time to maximum concentration [t_{max}], half-life)
- Safety and tolerability:
 - Continuous monitoring of adverse events
 - Laboratory safety tests [haematology, biochemistry and urinalysis]
 - 12-lead ECG (including QTcF and heart rate), supine vital signs [blood pressure and pulse rate]

- Peak (measured in first 4 hours after dosing) and AUC_{0-4h} pulse rate for each treatment period.
- Holter monitor results

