12.2 Pharmacodynamics

Cardiac Electrophysiology

In a multicenter, randomized, double-blind trial using tiotropium dry powder for inhalation that enrolled 198 patients with COPD, the number of subjects with changes from baseline-corrected QT interval of 30 to 60 msec was higher in the SPIRIVA HANDIHALER group as compared with placebo. This difference was apparent using both the Bazett (QTCB) [20 (20%) patients vs. 12 (12%) patients] and Fredericia (QTCF) [16 (16%) patients vs. 1 (1%) patient] corrections of QT for heart rate. No patients in either group had either QTcB or QTcF of >500 msec. Other clinical studies with SPIRIVA HANDIHALER did not detect an effect of the drug on QTc intervals.

The effect of tiotropium dry powder for inhalation on QT interval was also evaluated in a randomized, placebo- and positive-controlled crossover study in 53 healthy volunteers. Subjects received tiotropium dry powder for inhalation 18 mcg, 54 mcg (3 times the recommended dose), or placebo for 12 days. ECG assessments were performed at baseline and throughout the dosing interval following the first and last dose of study medication. Relative to placebo, the maximum mean change from baseline in study-specific QTc interval was 3.2 msec and 0.8 msec for tiotropium dry powder for inhalation 18 mcg and 54 mcg, respectively. No subject showed a new onset of QTc >500 msec or QTc changes from baseline of \geq 60 msec.

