2.2 Study Endpoints

The primary endpoints of the study are:

• Peak FEV₁ (measured in first 4 hours after dosing) and AUC_{0-12h} FEV₁. These will be measured after dosing on Day 3.

The secondary endpoints are:

- Determination of AUC_{0-4h} FEV₁ after morning dosing
- Peak FEV₁ (measured in first 4 hours after dosing) and AUC_{0-12h} FEV₁. These will be measured after dosing on Day 1
- Determination of onset of action (>10% increase in FEV₁, from pre-first dose, censored at 120 minutes) on Day 1
- RV, FRC, and sG_{aw} at 1.25 hours after dosing on Day 2
- RPL554 steady state pharmacokinetics (AUC, maximum observed concentration (C_{max}), time to maximum concentration (t_{max}), half-life)
- Safety and tolerability:
 - Continuous monitoring of adverse events
 - Laboratory safety tests [haematology, biochemistry and urinalysis]
 - 12-lead electrocardiogram (ECG) (including QT interval corrected using Fridericia's formula (QTcF) and heart rate), supine vital signs [blood pressure and pulse rate]
 - Peak (measured in first 4 hours after dosing) and AUC_{0-4h} pulse rate for each treatment period
 - Holter monitor results

The exploratory endpoints are:

- Pre-dose FEV₁ on Day 3

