6.18.4 Electrocardiography

The AUC parameters will be calculated using the linear trapezoidal rule. The peak heart rate will be computed as the maximum value in the 4 hours after dosing.

Peak (measured in first 4 hours after dosing) and AUC_{0-4h} heart rate will be derived.

ECG data including QTcF and heart rate data will be summarised and listed.

Shift table in relation to the normal range from baseline over time for the absolute values will be presented for ECG data. Number and percentage of subjects will be presented for the change from baseline values. The absolute values will be categorised as: \leq 450 msec, >450 msec, >480 msec and >500 msec. The change from baseline values will be categorised as: increase >30 msec and increase >60 msec.

Mean (±SEM) figures will be presented for changes from baseline QTcF and heart rate data for Day 1 and Day 3 separately. The three study treatments will be represented by different colours on the figures at each postdose timepoint.

All ECG overall interpretation data will be listed. Abnormal ECG data will be listed separately.

6.18.5 24-Hour Holter Monitoring

All 24-hour Holter monitoring and parameter data will be listed. Data for time in AFIB percentage, supraventricular runs, total QRS complexes, ventricular runs, ventricular singles and RR > 2 seconds will be summarised.

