6.18.7 Safety Analyses

Peak (measured in first 4 hours after dosing) and AUC_{0-4h} pulse rate and heart rate will be analysed.

Peak and AUC_{0-4h} for the pulse rate and heart rate will be analysed by comparing between the three study treatments using ANCOVA models with fixed factors for

treatment, period and patient, and using the baseline measurement of the treatment day (pre-first dose in a treatment period) as a covariate. The combination of tiotropium + RPL554 will be compared to tiotropium alone for each of the two doses of RPL554. Results of the comparisons will be expressed as the least squared means with 95% confidence interval (CI) and associated, 2-sided p-value.

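### The SAP plans no RPL554-minus-placebo difference in QTcF with a confidence interval, and it defines the ECG baseline in conflicting ways

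*Protocol*

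**What the plan says.** Protocol 10.3.2 lists among the secondary safety endpoints "12-lead ECG (including QTcF and heart rate), supine vital signs [blood pressure and pulse rate", and SAP 2.2 repeats it.

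The analysis then separates the two ECG variables. SAP 6.18.7 states "Peak (measured in first 4 hours after dosing) and AUC_{0-4h} pulse rate and heart rate will be analysed", using an ANCOVA with treatment, period and patient as fixed factors and a baseline covariate, each dose against tiotropium alone, with 95% CI and p-value. QTcF is not in that section. The protocol synopsis likewise lists blood pressure, pulse rate and ECG heart rate for additive models, without QTcF.

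For QTcF, SAP 6.18.4 says "ECG data including QTcF and heart rate data will be summarised and listed". It adds a shift table, absolute categories (up to 450, above 450, above 480 and above 500 msec), and "The change from baseline values will be categorised as: increase >30 msec and increase >60 msec". It also plans mean (SEM) change plots showing the three treatments on Days 1 and 3. All of this is per arm.

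The appended tiotropium label (Protocol 15.1, label section 12.2) says of one COPD trial that the "number of subjects with changes from baseline-corrected QT interval of 30 to 60 msec was higher in the SPIRIVA HANDIHALER group" than on placebo. By one correction it gives "Fredericia (QTCF) [16 (16%) patients vs. 1 (1%) patient".

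**The concern.** Each patient receives all three treatments, and the control is tiotropium + placebo. The design therefore supplies a within-patient QTcF contrast for each RPL554 dose on top of tiotropium. The SAP computes such a contrast for heart rate from the same ECGs but not for QTcF.

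A reader of the study report would have three columns of means and counts and no interval for their difference. An apparent rise could not be separated from noise, and an apparent absence of effect could not be bounded. The counts need particular care, because if the label's COPD trial is a guide, tiotropium alone can put patients into the 30 to 60 msec range.

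The baseline adds a second problem. If changes are taken from a value recorded after RPL554 has been given, the planned summaries, counts and plots can understate an RPL554 effect. This holds whether or not a model is fitted.

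**Working it through.** **1. The ECG baseline, side by side**

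| Place | Baseline |
|---|---|
| SAP 6.2, general rule | last non-missing value before study treatment in the period |
| SAP 6.2, ECG and vital signs | time-matched values from Day 1 of the period |
| SAP 6.18 | pre-dose value of each treatment day |
| SAP 6.18.7, model covariate | called the treatment-day value, but explained as pre-first-dose in the period |
| Protocol 10.4.7 | pre-dose value at each treatment visit |

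Protocol 7.4.5 schedules ECGs pre-dose, 2 h and 4 h on Day 1; pre-dose and 2 h on Day 2; and pre-dose, 2 h, 4 h and 24 h on Day 3. Day 1 has one pre-dose ECG, so a Day 1 value matched to 2 h or 4 h is post-dose.

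Let e1 and e5 be the RPL554 effect on QTcF, beyond tiotropium, at 2 h after the first dose (Day 1) and the fifth dose (Day 3). The expected arm difference in the Day 3, 2 h change is then:
- with the pre-first-dose Day 1 baseline: e5;
- with the time-matched Day 1 baseline: e5 − e1, which is zero if the effect is the same after both doses;
- with the Day 3 pre-dose baseline: e5 minus whatever effect remains 12 h after the fourth dose.

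On Day 1 itself the time-matched change is zero by construction.

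**2. The plan's own precision figure**

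Protocol 10.5 and SAP 3 give 24 patients, residual CV 6%, 80% power and a 5.1% difference in peak FEV1.
- Log-scale SD = √ln(1 + 0.06²) = 0.05995
- Difference = ln(1.051) = 0.0497
- SE = 0.05995 × √(2/24) = 0.0173
- Power = 80.2% (noncentral t, 43 df), or 82.0% by the normal approximation

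The figure reproduces. It concerns FEV1 only, but the same contrast formula applies to QTcF. The documents state no precision for QTcF.

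**3. Precision if QTcF joins the existing model**

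With 24 completers there are 72 observations per time point.
- Residual df = 72 − 1 − 23 (patients) − 2 (treatments) − 2 (periods) − 1 (covariate) = 43
- 95% half-width = t(0.975, 43) × SD × √(2/24) = 2.017 × 0.2887 × SD = 0.58 × SD

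The documents give no QTcF SD, so the SD below is an assumption.

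| Assumed within-patient residual SD (msec) | 6 | 8 | 10 | 12 | 15 |
|---|---|---|---|---|---|
| 95% half-width, 24 patients (msec) | 3.5 | 4.7 | 5.8 | 7.0 | 8.7 |
| 95% half-width, 30 patients (msec) | 3.1 | 4.1 | 5.2 | 6.2 | 7.8 |

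**4. Why the plotted SEMs do not supply this interval**

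If two arms each have standard error s and their changes correlate at ρ within patient, the SE of the difference is s√(2(1 − ρ)). A reader with only the two SEMs can form s√2, which is larger by 1/√(1 − ρ). At an assumed ρ of 0.3 that factor is 1.20, and at 0.5 it is 1.41. The value of ρ cannot be recovered from per-arm output.

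**5. What the counts can carry**

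At the label's 16%, 0.16 × 24 = 3.8 patients would show a 30 to 60 msec rise in each arm, tiotropium + placebo included. At its placebo rate of 1%, the figure is 0.24. The SAP plans no test on these counts. As a gauge of how little they resolve, a comparison of 16% with 30% at 24 per arm would have 21% power, and with 40% it would have 46%, treating the arms as independent.

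**The case against.** A reader might infer that the trial gives no estimate of RPL554's QTcF effect, or that tiotropium confounds it. The documents do not support either. All three arms receive tiotropium, so its contribution cancels in expectation against tiotropium + placebo. The planned arm means already allow an unadjusted point difference by subtraction, and each RPL554 count stands beside a placebo count.

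The label evidence is also mixed. It covers 30 to 60 msec changes, not larger ones, and says that other tiotropium studies detected no QTc effect. Its crossover QT study in 53 volunteers found a maximum mean change against placebo of 3.2 msec at 18 mcg, with no change of 60 msec or more. Applying the 16% to a few ECGs over three days is an assumption.

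Nor can the baseline be called tiotropium-free. Protocol 5.9.1 does say "All long acting (once or twice daily) bronchodilators will be stopped at the screening visit and are not allowed during the study", but two of the baseline rules above use values recorded after study dosing. Protocol 3.2 gives tiotropium a half-life of 5 to 6 days, which would leave 38 to 45% after 7 days (0.5^(7/5) and 0.5^(7/6)). The label's 25 h, given for 5 mcg, would leave about 1%.

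It can further be said that the SAP follows the protocol's list of modelled variables, that the trial was sized on FEV1, and that the heart-rate increases in Protocol 1.2 were at 12 to 24 mg, above both doses studied here. SAP 6.12.1 says that continuous variables will be compared by ANCOVA, which might seem to cover QTcF. However, that is a multiplicative model, and SAP 6.12 refers safety to its own section.

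These points limit the claim. They do not supply a planned difference, an interval or a single baseline.

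**Conclusion.** The point holds in limited form. QTcF is a named safety endpoint with no planned between-treatment estimate and no confidence interval, and per-arm SEMs cannot replace one because they ignore the crossover pairing. Separately, the ECG baseline rules contradict each other, and some of them would subtract part of RPL554's own effect.

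The model already in SAP 6.18.7 would bound each dose's QTcF effect to about ±3.5 to ±8.7 msec with 24 completers. This rests on an assumed residual SD of 6 to 15 msec and on using the pre-first-dose baseline. The need for the contrast does not depend on whether the tiotropium background is 16% or 1%. The change is worth making before database lock. The finding is not that the trial is uninformative on QTcF or biased by tiotropium.

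**What to change.** - **SAP 6.18.7:** add QTcF to the additive ANCOVA (treatment, period, patient, baseline), fitted separately at 2 h and 4 h on Days 1 and 3 and at 2 h on Day 2. Report RPL554 6 mg and 1.5 mg, each minus tiotropium + placebo, with 95% CI, as descriptive safety evidence. The Day 3 24 h ECG can stay in the summaries.
- **SAP 6.2, 6.18 and 6.18.4:** use one ECG baseline, the pre-first-dose Day 1 value of each period, for the model covariate, changes, counts and plots.
- **SAP 6.18.4:** keep the counts above 30 and 60 msec as supportive, read beside the tiotropium + placebo count. Rest any statement about RPL554 and QTcF on the placebo-corrected difference.
- **SAP 6.19:** record the addition as a change from the protocol's planned analysis.

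The cost is SAP wording and five fits of a model already specified, on ECGs already scheduled. No patients, visits or procedures are added. The small downside is 5 × 2 = 10 more unadjusted intervals, which fits the descriptive status that SAP 6.15 gives to secondary endpoints.

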12.3 Pharmacokinetics

Tiotropium is administered by dry powder inhalation. Some of the pharmacokinetic data described below were obtained with higher doses than recommended for therapy. A dedicated pharmacokinetic study in patients with COPD evaluating once-daily tiotropium delivered from the RESPIMAT inhaler (5 mcg) and as inhalation powder (18 mcg) from the HANDIHALER device resulted in a similar systemic exposure between the two products.

Absorption

Following dry powder inhalation by young healthy volunteers, the absolute bioavailability of 19.5% suggests that the fraction reaching the lung is highly bioavailable. Oral solutions of tiotropium have an absolute bioavailability of 2-3%. Food is not expected to influence the absorption of tiotropium. Maximum tiotropium plasma concentrations were observed 7 minutes after inhalation.

Distribution

Tiotropium is 72% bound to plasma protein and had a volume of distribution of 32 L/kg after intravenous administration to young healthy volunteers. Local concentrations in the lung are not known, but the mode of administration suggests substantially higher concentrations in the lung. Studies in rats have shown that tiotropium does not readily penetrate the blood-brain barrier.

Elimination

The terminal half-life of tiotropium in COPD patients following once daily inhalation of 5 mcg tiotropium was approximately 25 hours. Total clearance was 880 mL/min after intravenous administration in young healthy volunteers. After chronic once-daily dry powder inhalation by COPD patients, pharmacokinetic steady state was reached by day 7 with no accumulation thereafter.

Metabolism

The extent of metabolism is small. This is evident from a urinary excretion of 74% of unchanged substance after an intravenous dose to young healthy volunteers. Tiotropium, an ester, is nonenzymatically cleaved to the alcohol N-methylscopine and dithienylglycolic acid, neither of which binds to muscarinic receptors.

In vitro experiments with human liver microsomes and human hepatocytes suggest that a fraction of the administered dose (74% of an intravenous dose is excreted unchanged in the urine, leaving 25% for metabolism) is metabolized by cytochrome P450-dependent oxidation and subsequent glutathione conjugation to a variety of Phase II metabolites. This enzymatic pathway can be inhibited by CYP450 2D6 and 3A4 inhibitors, such as quinidine, ketoconazole, and gestodene. Thus, CYP450 2D6 and 3A4 are involved in the metabolic pathway that is responsible for the elimination of a small part of the administered dose. In vitro studies using human liver microsomes showed that tiotropium in supra-therapeutic concentrations did not inhibit CYP450 1A1, 1A2, 2B6, 2C9, 2C19, 2D6, 2E1, or 3A4.

*Excretion*Intravenously administered tiotropium bromide is mainly excreted unchanged in urine (74%). After dry powder inhalation to COPD patients at steady state, urinary excretion was 7% ($1.3 \mu g$) of the unchanged dose over 24 hours. The renal clearance of tiotropium exceeds the creatinine clearance, indicating secretion into the urine.

Specific Populations

Geriatric Patients

As expected for all predominantly renally excreted drugs, advancing age was associated with a decrease of tiotropium renal clearance (365 mL/min in COPD patients <65 years to 271 mL/min in COPD patients <65 years). This did not result in a corresponding increase in AUC_{0-6,11} and C_{max,12} values following administration via HANDIHALER device.

Renal Impairment

Following 4-week SPIRIVA HANDIHALER or SPIRIVA RESPIMAT once daily dosing in patients with COPD, mild renal impairment (creatinine clearance 60-90 mL/min) resulted in 6-23% higher $AUC_{0-6,sx}$ and 6-17% higher $C_{max,sx}$ values; moderate renal impairment (creatinine clearance 30-60 mL/min) resulted in 54-57% higher $AUC_{0-6,sx}$ and 15-31% higher $C_{max,sx}$ values compared to COPD patients with normal renal function (creatinine clearance >90 mL/min). There is insufficient data for tiotropium exposure in patients with severe renal impairment (creatinine clearance <30 mL/min) following inhalation of SPIRIVA HANDIHALER or SPIRIVA RESPIMAT. However AUC_{0-4} and C_{max} were 94% and 52% higher, respectively, in patients with severe renal impairment following intravenous infusion of tiotropium bromide.

Hepatic Impairment

The effects of hepatic impairment on the pharmacokinetics of tiotropium were not studied.

Drug Interactions

An interaction study with tiotropium (14.4 mcg intravenous infusion over 15 minutes) and cimetidine 400 mg three times daily or ranitidine 300 mg once daily was conducted. Concomitant administration of cimetidine with tiotropium resulted in a 20% increase in the AUC_{0-4b}, a 28% decrease in the renal clearance of tiotropium and no significant change in the C_{max} and amount excreted in urine over 96 hours. Co-administration of tiotropium with ranitidine did not affect the pharmacokinetics of tiotropium.

Common concomitant medications (long-acting beta2-adrenergic agonists (LABA), inhaled corticosteroids (ICS)) used by patients with COPD were not found to alter the exposure to tiotropium.

13 NONCLINICAL TOXICOLOGY

13.1 Carcinogenesis, Mutagenesis, Impairment of Fertility

No evidence of tumorigenicity was observed in a 104-week inhalation study in rats at tiotropium doses up to 59 mcg/kg/day, in an 83-week inhalation study in female mice at doses up to 145 mcg/kg/day, and in a 101-week inhalation study in male mice at doses up to 2 mcg/kg/day. These doses correspond to approximately 30, 40, and 0.5 times the recommended human daily inhalation dose (MRHDID) on a mcg/m² basis, respectively.

Tiotropium bromide demonstrated no evidence of mutagenicity or clastogenicity in the following assays: the bacterial gene mutation assay, the V79 Chinese hamster cell mutagenesis assay, the chromosomal aberration assays in human lymphocytes *in vitro* and mouse micronucleus formation *in vivo*, and the unscheduled DNA synthesis in primary rat hepatocytes *in vitro* assay.

In rats, decreases in the number of corpora lutea and the percentage of implants were noted at inhalation tiotropium doses of 78 mcg/kg/day or greater (approximately 40 times the MRHDID on a mcg/m² basis). No such effects were observed at 9 mcg/kg/day (approximately 5 times the MRHDID on a mcg/m² basis). The fertility index, however, was not affected at inhalation doses up to 1689 mcg/kg/day (approximately 910 times the MRHDID on a mcg/m² basis).

14 CLINICAL STUDIES

The SPIRIVA HANDIHALER (tiotropium bromide inhalation powder) clinical development program consisted of six Phase 3 studies in 2663 patients with COPD (1308 receiving SPIRIVA HANDIHALER): two 1-year, placebo-controlled studies, two 6-month, placebo-controlled studies and two 1-year, ipratropium-controlled studies. These studies enrolled patients who had a clinical diagnosis of COPD, were 40 years of age or older, had a history of smoking greater than 10 pack-years, had a forced expiratory volume in one second (FEV1) less than or equal to 60% or 65% of predicted, and a ratio of FEV1/FVC of less than or equal to 0.7.

In these studies, SPIRIVA HANDIHALER, administered once-daily in the morning, provided improvement in lung function (FEV1), with peak effect occurring within 3 hours following the first dose.

Two additional trials evaluated exacerbations: a 6-month, randomized, double-blind, placebo-controlled, multicenter clinical trial of 1829 COPD patients in a US Veterans Affairs setting and a 4-year, randomized, double-blind, placebo-controlled, multicenter, clinical trial of 5992 COPD patients. Long-term effects on lung function and other outcomes, were also evaluated in the 4-year multicenter trial.

6-Month to 1-Year Effects on Lung Function

In the 1-year, placebo-controlled trials, the mean improvement in FEV₁ at 30 minutes was 0.13 liters (13%) with a peak improvement of 0.24 liters (24%) relative to baseline after the first dose (Day 1). Further improvements in FEV₁ and forced vital capacity (FVC) were observed with pharmacodynamic steady state reached by Day 8 with once-daily treatment. The mean peak improvement in FEV₁, relative to baseline, was 0.28 to 0.31 liters (28% to 31%), after 1 week (Day 8) of once-daily treatment. Improvement of lung function was maintained for 24 hours after a single dose and consistently maintained over the 1-year treatment period with no evidence of tolerance.

In the two 6-month, placebo-controlled trials, serial spirometric evaluations were performed throughout daytime hours in Trial A (12 hours) and limited to 3 hours in Trial B. The serial FEV1 values over 12 hours (Trial A) are displayed in Figure 1. These trials further support the improvement in pulmonary function (FEV1) with SPIRIVA HANDIHALER, which persisted over the spirometric observational period. Effectiveness was maintained for 24 hours after administration over the 6-month treatment period.

*Means adjusted for center, treatment, and baseline effect. On Day 169, a total of 183 and 149 patients in the SPIRIVA HANDIHALER and placebo groups, respectively, completed the trial. The data for the remaining patients were imputed using the last observation or least favorable observation carried forward.

Results of each of the 1-year ipratropium-controlled trials were similar to the results of the 1-year placebo-controlled trials. The results of one of these trials are shown in Figure 2.

*Means adjusted for center, treatment, and baseline effect. On Day 92 (primary endpoint), a total of 151 and 69 patients in the SPIRIVA HANDIHALER and ipratropium groups, respectively, completed through 3 months of observation. The data for the remaining patients were imputed using the last observation or least favorable observation carried forward.

A randomized, placebo-controlled clinical study in 105 patients with COPD demonstrated that bronchodilation was maintained throughout the 24-hour dosing interval in comparison to placebo, regardless of whether SPIRIVA HANDIHALER was administered in the morning or in the evening.

Throughout each week of the 1-year treatment period in the two placebo-controlled trials, patients taking SPIRIVA HANDIHALER had a reduced requirement for the use of rescue short-acting beta2-agonists, as compared to placebo, was demonstrated in one of the two 6-month studies.

4-Year Effects on Lung Function

A 4-year, randomized, double-blind, placebo-controlled, multicenter clinical trial involving 5992 COPD patients was conducted to evaluate the long-term effects of SPIRIVA HANDIHALER on disease progression (rate of decline in FEV₁). Patients were permitted to use all respiratory medications (including short-acting and long-acting beta-agonists, inhaled and systemic steroids, and theophyllines) other than inhaled anticholinergics. The patients were 40 to 88 years of age, 75% male, and 90% Caucasian with a diagnosis of COPD and a mean pre-bronchodilator FEV₁ of 39% predicted (range = 9% to 76%) at study entry. There was no difference between the groups in either of the co-primary efficacy endpoints, yearly rate of decline in pre- and post-bronchodilator FEV₁, as demonstrated by similar slopes of FEV₁ decline over time (Figure 3).

SPIRIVA HANDIHALER maintained improvements in trough (pre-dose) FEV₁ (adjusted means over time: 87 to 103 mL) throughout the 4 years of the study (Figure 3).

Figure 3 Trough (pre-dose) FEV1 Mean Values at Each Time Point

Repeated measure ANOVA was used to estimate means. Means are adjusted for baseline measurements. Baseline trough FEV₁ (observed mean) = 1.12. Patients with \geq 3 acceptable pulmonary function tests after Day 30 and non-missing baseline value were included in the analysis.

Exacerbations

The effect of SPIRIVA HANDIHALER on COPD exacerbations was evaluated in two clinical trials: a 4-year clinical trial described above and a 6-month clinical trial of 1829 COPD patients in a Veterans Affairs setting. In the 6-month trial, COPD exacerbations were defined as a complex of respiratory symptoms (increase or new onset) of more than one of the following: cough, sputum, wheezing, dyspnea, or chest tightness with a duration of at least 3 days requiring treatment with antibiotics, systemic steroids, or hospitalization. The population had an age ranging from 40 to 90 years with 99% males, 91% Caucasian, and had COPD with a mean pre-

bronchodilator FEV₁ percent predicted of 36% (range = 8% to 93%). Patients were permitted to use respiratory medications (including short-acting and long-acting beta-agonists, inhaled and systemic steroids, and theophyllines) other than inhaled anticholinergics. In the 6-month trial, the co-primary endpoints were the proportion of patients with COPD exacerbation and the proportion of patients with hospitalization due to COPD exacerbation. SPIRIVA HANDIHALER significantly reduced the proportion of COPD patients who experienced exacerbations compared to placebo (27.9% vs. 32.3%, respectively; Odds Ratio (OR) (tiotropium/placebo) = 0.81; 95% CI = 0.66, 0.99; p = 0.037). The proportion of patients with hospitalization due to COPD exacerbations in patients who used SPIRIVA HANDIHALER compared to placebo was 7.0% vs. 9.5%, respectively; OR = 0.72; 95% CI = 0.51, 1.01; p = 0.056.

Exacerbations were evaluated as a secondary outcome in the 4-year multicenter trial. In this trial, COPD exacerbations were defined as an increase or new onset of more than one of the following respiratory symptoms (cough, sputum, sputum purulence, wheezing, dyspnea) with a duration of three or more days requiring treatment with antibiotics and/or systemic (oral, intranuscular, or intravenous) steroids. SPIRIVA HANDIHALER significantly reduced the risk of an exacerbation by 14% (Hazard Ratio (HR) = 0.86; 95% CI = 0.81, 0.91; p<0.001) and reduced the risk of exacerbation-related hospitalization by 14% (HR = 0.86; 95% CI = 0.78, 0.95; p<0.002) compared to placebo. The median time to first exacerbation was delayed from 12.5 months (95% CI = 11.5, 13.8) in the placebo group to 16.7 months (95% CI = 14.9, 17.9) in the SPIRIVA HANDIHALER group.

All-Cause Mortality

In the 4-year placebo-controlled lung-function trial described above, all-cause mortality compared to placebo was assessed. There were no significant differences in allcause mortality rates between SPIRIVA HANDIHALER and placebo.

The all-cause mortality of SPIRIVA HANDIHALER was also compared to tiotropium inhalation spray 5 mcg (SPIRIVA RESPIMAT 5 mcg) in an additional longterm, randomized, double-blind, double-dummy active-controlled study with an observation period up to 3 years. All-cause mortality was similar between SPIRIVA HANDIHALER and SPIRIVA RESPIMAT.

